
## **Study Objectives and Endpoints**

### **Primary Objective**

To demonstrate that treatment with avelumab in combination with standard of care (SOC) CRT is superior to SOC CRT alone in prolonging progression-free survival (PFS) in front-line patients with high-risk (as defined in Inclusion Criterion 2 [Section 4.1]), locally advanced SCCHN who are candidates for definitive CRT with cisplatin.

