### 4.1. Inclusion Criteria

Patient eligibility should be reviewed and documented by an appropriate member of the investigator's study team before patients are included in the study.

Patients must meet all of the following inclusion criteria to be eligible for enrollment into the study:

4. Histological diagnosis of squamous cell carcinoma of the oral cavity, oropharynx, hypopharynx, or larynx with tissue available.
5. High-risk disease as defined by American Joint Committee on Cancer [AJCC] Guidelines 7th Edition:

- HPV-negative disease, Stage III, IVa, IVb per tumor/nodes/metastasis (TNM) guidelines for head and neck sites; or
- Non-oropharyngeal HPV-positive disease, Stage III, IVa, IVb per TNM guidelines for head and neck sites; or
- HPV-positive oropharyngeal disease T4 OR N2c OR N3 per TNM guidelines for head and neck sites.

where HPV status will be determined per institutional standard using p16 immunohistochemistry (IHC).

6. No prior therapy for advanced stage SCCHN; eligible for definitive CRT with curative intent.
7. Available tumor samples for submission or willing to undergo further tumor biopsies:
  - Availability of a formalin-fixed paraffin-embedded (FFPE) tumor tissue block from primary tumor or nodal biopsy. If an FFPE tissue block cannot be provided, 15 unstained slides (10 minimum) will be acceptable.
8. Age  $\geq 18$  years ( $\geq 20$  years in Japan and Taiwan, and  $\geq 19$  years in Korea).
9. Eastern Cooperative Oncology Group (ECOG) Performance Status (PS) 0 or 1 ([Appendix 2](#)).

10. Adequate bone marrow function, including:

- Absolute Neutrophil Count (ANC)  $\geq 1,800/\mu\text{L}$  or  $\geq 1.8 \times 10^9/\text{L}$ .
- Platelets  $\geq 100,000/\mu\text{L}$  or  $\geq 100 \times 10^9/\text{L}$ .
- Hemoglobin  $\geq 9$  g/dL (may have been transfused).

11. Adequate renal function, including:

- Estimated creatinine clearance  $\geq 50$  mL/min as calculated using the Cockcroft-Gault (CG) equation OR;
- A creatinine clearance of at least 60 ml/min if this value is described in the contra-indications for cisplatin as per country's local labeling.

12. Adequate liver function, including:

- Total serum bilirubin  $\leq 1.5$  x upper limit of normal (ULN).
- Aspartate and alanine aminotransferase (AST and ALT)  $\leq 2.5$  x ULN.

13. Pregnancy test (for patients of childbearing potential) negative at screening.

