#### **5.5.2.2. Cisplatin Dose Modifications for Toxicity During Concurrent Radiation**

Patients will be examined and graded for subjective/objective evidence of toxicity while receiving concurrent cisplatin with radiotherapy.

Chemotherapy dosage modifications are based upon laboratory values obtained within the 24 hours prior to cisplatin and non-hematologic toxicities during the week prior to a particular cisplatin dose. Laboratory draws can be performed 1 business day prior to cisplatin infusion ie, laboratory draws on Friday can be used for infusion on Monday providing that any abnormality compromising cisplatin infusion (eg neutropenia, creatinine increase) is re-assessed on the day of infusion.

The dose modifications for cisplatin (below) are intended to be permanent (ie, if the patient's dose is reduced to dose level -1, it remains at the reduced dose level for the remainder of the CRT Phase). There will be no dose re-escalation for cisplatin.

The dose of cisplatin may be modified on Days 22 and/or 43 for the following toxicities:

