**5.5.2.2.2. Cisplatin-Related Non-Hematologic Adverse Events**

*Neutropenic Fever*

Temperature of 38.5°C with ANC  $< 1000/\text{mm}^3$  is an expected potential complication of concurrent chemotherapy and radiotherapy or chemotherapy alone. If neutropenic fever is encountered, then the chemotherapy dose reduction will be determined by the weekly blood counts (see Table 9).

*Renal Toxicity*

Cisplatin dose should be based on the serum creatinine or creatinine clearance immediately prior to the second cisplatin dose using the following guidelines. Note: If creatinine is  $> 1.5$  mg/dL, creatine clearance must be calculated (Cockcroft-Gault) in order to make a dose adjustment. If the calculated clearance is  $\geq 50$  mL/min, a 24-hour urine collection is not needed. However, if the calculation is  $< 50$  mL/min, a 24-hour urine collection is required, and the cisplatin dose will be determined as described in [Table 10](#).

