**Table 10. Cisplatin Dose Modification Due to Decreased Creatinine Clearance**

Serum Creatinine		Creatinine Clearance	Cisplatin Dose
≤1.5 mg/dL	OR	>50 mL/min	100 mg/m 
>1.5 mg/dL	AND	40-50 mL/min	50 mg/m 
>1.5 mg/dL	AND	< 40 mL/min	Hold cisplatin a

a. Cisplatin should be held (but the RT continued) and the creatinine measured weekly, until it is <1.5 mg/dL or the creatinine clearance is >50 mL/min, and then the second dose of cisplatin should be given at the reduced dose of 50 mg/m^2.

*Neurologic (Neuropathy) Adverse Events:*

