**Table 11. Cisplatin Dose Modifications Due to Neurologic Toxicity**

CTCAE Grade	Dose Reduction
0 – 1	None
2	One dose level
3 – 4	Hold drug

*Ototoxicity:*

Should patients develop clinical evidence of ototoxicity, further audiometric evaluation is required. A neurologic deficit should be distinguished from a conductive loss from obstruction of the Eustachian tube leading to a middle ear effusion. Because no AE scale, including the CTCAE, v4.03, has been validated in terms of correlation with clinically relevant hearing loss, there are no protocol mandates requiring dose reduction for audiogram-determined sensorineural hearing loss without an analogous clinical high grade (>Grade 2) hearing loss. However, for clinical Grade 3 or higher hearing loss, cisplatin should be held and for Grade 2 clinical hearing loss, one dose level reduction.

Dependent upon the requirements documented in each country's cisplatin SmPC, patients may require a baseline audiogram and a second audiogram within 12 weeks after the completion of CRT to monitor for potential ototoxicity related to cisplatin administration. Audiograms are a requirement in France. For other countries that may have this requirement for cisplatin administration, refer to the local cisplatin SmPC.

*All Other Non-Hematologic Adverse Events Attributable to Cisplatin during Concurrent Radiation:*

For Grade>2 toxicities (excluding lymphopenia, mucositis, or dysphagia), hold cisplatin, re-evaluate weekly until AE resolves to Grade ≤1, then restart cisplatin at one lower dose level.

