#### **5.10. Potential for Drug-Drug Interactions with Cisplatin**

Plasma levels of anticonvulsant agents may become subtherapeutic during cisplatin therapy.

Cisplatin might reduce the absorption of phenytoin thereby leading to reduced control of epilepsy. Per country's product labeling, anti-seizure medication might have to be changed to an alternative that is not contra-indicated with cisplatin administration.

In a randomized trial in advanced ovarian cancer, response duration was adversely affected when pyridoxine was used in combination with altretamine (hexamethylmelamine) and cisplatin.

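### As printed, the renal inclusion criterion admits patients with creatinine clearance of 50 to below 60 mL/min in countries whose cisplatin label contraindicates use below 60

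*Protocol*

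**What the plan says.** Section 4.1 of the protocol requires every numbered inclusion criterion to be met. The adequate renal function criterion, printed as number 11, has two bullets. The first sets an estimated creatinine clearance of at least 50 mL/min, "as calculated using the Cockcroft-Gault (CG) equation OR". It has no country restriction. The second reads "A creatinine clearance of at least 60 ml/min if this value is described in the contra-indications for cisplatin", with reference to the country's local labeling. It names no method of measurement.

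The renal rules for cisplatin dosing come later. Section 5.5.2.2 opens them with "The dose of cisplatin may be modified on Days 22 and/or 43 for the following toxicities". The renal toxicity paragraph in Section 5.5.2.2.2 bases the dose on renal function "immediately prior to the second cisplatin dose using the following guidelines". Table 10 has cut-points at 50 and 40 mL/min only, and its footnote keeps cisplatin on hold "until it is <1.5 mg/dL or the creatinine clearance is >50 mL/min".

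The protocol defers to local cisplatin labeling on two other matters: audiograms, in the ototoxicity text of Section 5.5.2.2.2 ("For other countries that may have this requirement for cisplatin administration, refer to the local cisplatin SmPC"), and anticonvulsants, in Section 5.10 ("Per country's product labeling, anti-seizure medication might have to be changed"). Neither concerns renal function.

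**The concern.** The second bullet appears to be meant to raise the entry limit where a national label is stricter. Joined by OR to an unrestricted limit of 50, it cannot do that, because an alternative can only widen a criterion. In a country whose label contraindicates cisplatin below 60 mL/min, a patient at 55 satisfies the renal criterion as printed.

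Cisplatin 100 mg/m² is the backbone drug in both arms. If the criterion is followed to the letter, the only numerical clearance check before the first dose passes a patient whom the local label contraindicates.

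There is also a smaller matter of consistency. SAP Section 6.5.2.2 reports patients who were dosed without satisfying the inclusion criteria. A patient at 55 mL/min in such a country is not a deviation under the printed wording, but is one under the likely intent, so two sites could classify identical patients differently.

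**Working it through.** The documents give no numerical result to reproduce here. The check is one of logic, followed by a search for the 60 mL/min limit elsewhere.

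**Step 1. The rule as printed.** Inputs are the two bullets in Section 4.1. Let C be the clearance, measured the same way for both bullets, in a country whose label states 60.

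- Printed rule: (C ≥ 50) OR (C ≥ 60). Any C of at least 60 is also at least 50, so this reduces to C ≥ 50.
- Replacement rule: C ≥ 60.

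| C (mL/min) | First bullet | Second bullet | Printed rule | Replacement rule |
|---|---|---|---|---|
| 45 | no | no | ineligible | ineligible |
| 50 | yes | no | **eligible** | **ineligible** |
| 55 | yes | no | **eligible** | **ineligible** |
| 59 | yes | no | **eligible** | **ineligible** |
| 60 | yes | yes | eligible | eligible |
| 65 | yes | yes | eligible | eligible |

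The two rules differ only for 50 ≤ C < 60. In a country whose label does not state 60, both give C ≥ 50 and nothing changes.

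**Step 2. Different methods for the two bullets.** The second bullet does not specify Cockcroft-Gault. A patient with a Cockcroft-Gault value of 48 and a value of 62 by another method fails the first bullet and passes the second, so is eligible as printed. The second bullet can therefore add patients but never remove one.

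**Step 3. Whether the dosing rules supply the limit.** They begin at Day 22, so they do not govern the Day 1 dose. Applying Table 10 to whole-number clearances from 50 to 59 shows what would happen at the second dose:

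- 51 to 59 (9 of 10 values): 100 mg/m², whatever the serum creatinine.
- 50: 100 mg/m² if creatinine is at most 1.5 mg/dL; 50 mg/m² if it is above 1.5 mg/dL.
- Held: 0 of 10.

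The table has no country condition.

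**Step 4. Whether any other text states 60 mL/min.** The general suitability statement in Section 4, the requirement in Section 4.1 to be eligible for definitive chemoradiotherapy, and exclusion criterion 15 in Section 4.2 give no clearance value. Nor does the primary objective, which describes the population as "locally advanced SCCHN who are candidates for definitive CRT with cisplatin". The SAP per-protocol exclusions (Section 4.3.1) contain no renal rule. The value 60 appears elsewhere only in the amendment history, which is not current text.

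**Step 5. How the same list words similar rules.** The disease-stage bullets joined by or are true alternatives: any one suffices. The age criterion states its country-specific limits directly, with higher minimum ages for Japan, Taiwan and Korea. A site that reads the list consistently has grounds to treat the renal bullets as alternatives too.

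**The case against.** The strongest reply is that the intended meaning is clear. The second bullet carries its own condition, the content of the local label, so the natural reading is 50 by default and 60 where the label says so. The literal reading leaves the second bullet with almost no function. On this view the fault is a loose connector and the remedy is editorial.

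Other protections also exist. Footnote 8 of the first Schedule of Activities requires a core chemistry panel, which includes creatinine (Table 12), to be reviewed by the treating physician before dosing on Day 1 of the chemoradiotherapy phase. Section 5.5.2.2 asks for re-assessment on the day of infusion if earlier bloods showed an abnormality that compromises cisplatin. Section 5.4.2 makes the cisplatin package insert the reference safety document, and Section 12.2 requires compliance with legal and regulatory requirements. An investigational product manual, not available to us, covers administration. Finally, no participating country with a 60 mL/min label is identified, so the affected group may be empty.

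Much of this stands: the probable intent, the general safeguards and the possibly empty band are all accepted. But none of the protections available to read contains a clearance threshold, and the cited insert may not be each country's label. A patient in the band is stopped only by clinical judgment, by a site applying the intended reading, or by a check of the local label. A safety limit in an international trial should not depend on sites inferring what was meant.

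**Conclusion.** The concern holds. As printed, the 60 mL/min limb excludes no one, and no other current text states it as binding. The size is a band of 50 to below 60 mL/min in countries whose cisplatin label contraindicates use below 60; elsewhere the criterion is unaffected. The number of patients in the band is unknown and may be zero.

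The conclusion assumes the literal reading of OR, and assumes that some participating country has such a label, which the documents do not confirm. It is a fault in eligibility and safety wording that should be corrected. No sample size, power, alpha or bias consequence is claimed.

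**What to change.** Replace the two bullets with one statement:

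> Estimated creatinine clearance ≥50 mL/min by Cockcroft-Gault; in countries where the local cisplatin label contraindicates use below 60 mL/min, creatinine clearance must instead be ≥60 mL/min, by the method the local label specifies or otherwise by Cockcroft-Gault.

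This is one sentence in an amendment or clarification letter. The cost is that a small, unquantified number of patients at 50 to below 60 mL/min in those countries become ineligible.

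The documents do not say whether enrolment is still open. If it is closed, the wording change has no effect. In that case, list the randomized patients in the band in those countries and record whether each received cisplatin.

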#### 4.2. Exclusion Criteria

Patients with any of the following characteristics/conditions will not be included in the study:

1. Prior immunotherapy with an anti-PD-1, anti-PD-L1, anti-PD-L2, anti-CD137, or anti-CTLA-4 antibody (including ipilimumab), or any other antibody or drug specifically targeting T cell co-stimulation or immune checkpoint pathways.
2. Major surgery  $\leq 4$  weeks prior to randomization.
3. Prior malignancy (other than the current Head and Neck cancer or in situ disease) requiring tumor-directed therapy within the last 2 years prior to enrollment, or concurrent malignancy associated with clinical instability. Exceptions for disease within the 2 years are superficial esophageal cancer (TIS or T1a) fully resected by endoscopy, prostate cancer (Gleason score  $\leq 6$ ) either curatively treated or deemed to not require treatment, ductal in situ carcinoma of the breast that has completed curative treatment, adequately treated basal cell or squamous cell skin cancer.
4. Active autoimmune disease that might deteriorate when receiving an immunostimulatory agent. Patients with diabetes type I, vitiligo, psoriasis, or hypo- or hyperthyroid disease not requiring immunosuppressive treatment are eligible.
5. Any of the following in the 6 months prior to randomization: myocardial infarction, severe/unstable angina, coronary/peripheral artery bypass graft, symptomatic congestive heart failure, cerebrovascular accident, transient ischemic attack, or symptomatic pulmonary embolism.
6. Active infection requiring systemic therapy.
7. Known prior severe hypersensitivity to investigational products or any component in the formulations, including known severe hypersensitivity reactions to mAbs, cisplatin, or platinum-related compounds (NCI CTCAE v4.03 Grade  $\geq 3$ ).
8. Use of immunosuppressive medication at time of randomization, except the following:
  - a. Intranasal, inhaled, topical steroids, or local steroid injections (eg, intra-articular injection);
  - b. Systemic corticosteroids at physiologic doses  $\leq 10$  mg/day of prednisone or equivalent;
  - c. Steroids as premedication for hypersensitivity reactions (eg, CT scan premedication).
9. Prior organ transplantation including allogenic stem-cell transplantation.

10. Diagnosis of prior immunodeficiency or known human immunodeficiency virus (HIV) or acquired immunodeficiency syndrome (AIDS) related illness.
11. Hepatitis B virus (HBV) or hepatitis C virus (HCV) infection at screening (positive HBV surface antigen or HCV RNA [ribonucleic acid] if anti-HCV antibody screening test positive).
12. Vaccination within 4 weeks prior to randomization except for administration of inactivated vaccines.
13. Current use of or anticipated need for treatment with other anti-cancer drugs.
14. Pregnant female patients, breastfeeding female patients, and male patients able to father children and female patients of childbearing potential who are unwilling or unable to use 2 methods of contraception (at least one of which is considered to be highly effective) as outlined in the protocol for the duration of the study and for at least 6 months after the last dose of cisplatin and 30 days after the last dose of avelumab/placebo (whichever is later).
15. Other severe acute or chronic medical conditions including: immune colitis, inflammatory bowel disease, pneumonitis, pulmonary fibrosis, or psychiatric condition including recent (within the past year) or active suicidal ideation or behavior; or laboratory abnormality that may increase the risk associated with study participation or study treatment administration or may interfere with the interpretation of study results and, in the judgment of the investigator, would make the patient inappropriate for entry into this study.
16. Patients who are investigational site staff members directly involved in the conduct of the study and their family members, site staff members otherwise supervised by the investigator, or patients who are Pfizer employees directly involved in the conduct of the study.
17. Participation in other interventional studies involving investigational drug(s) within 4 weeks prior to randomization.

### **4.3. Lifestyle Guidelines**

In this study, male patients who are able to father children and female patients who are of childbearing potential will receive radiation and cisplatin and half of these patients will also receive avelumab. The effect of avelumab on reproduction is unknown. Cisplatin can cause fetal harm when administered to pregnant women.

Subjects who are, in the opinion of the investigator, sexually active and at risk for pregnancy must agree to use 2 methods of contraception (at least one of which is considered to be highly effective with low user dependency as defined below) throughout the study and continue to do so for at least 6 months after the last dose of cisplatin and 30 days after the last dose of avelumab/placebo (whichever is later). The investigator or his or her designee, in

consultation with the patient, will confirm the patient has selected 2 appropriate methods of contraception for the individual patient and his/her partner from the list of permitted contraception methods (see below) and will confirm the patient has been instructed in their consistent and correct use. Patients need to affirm that they meet the criteria for correct use of 2 of the selected methods of contraception. The investigator or his or her designee will discuss with the patient the need to use 2 contraception methods consistently and correctly according to the [Schedule of Activities](#) and document such conversation in the patient's chart. In addition, the investigator or his or her designee will instruct the patient to call immediately if one or both selected contraception methods are discontinued, or if pregnancy is known or suspected in the patient or the patient's partner.

Highly effective contraception methods with low user dependency include (applies to female subjects at risk for pregnancy with their male partners):

1. Established use of hormonal methods of contraception associated with inhibition of ovulation (eg, inserted, injected, implanted).
2. Correctly placed intrauterine device (IUD) or intrauterine system (IUS).
3. Male sterilization with absence of sperm in the post-vasectomy ejaculate.
4. Bilateral tubal ligation/bilateral salpingectomy or bilateral tubal occlusive procedure (provided that occlusion has been confirmed in accordance with the device's label).

Female patients of non-childbearing potential must meet at least one of the following criteria:

- Have undergone a documented hysterectomy and/or bilateral oophorectomy;
- Have medically confirmed ovarian failure; or
- Achieved postmenopausal status, defined as follows: cessation of regular menses for at least 12 consecutive months with no alternative pathological or physiological cause; status may be confirmed with a serum FSH level consistent with the post-menopausal state.

All other female patients (including females with tubal ligations) will be considered to be of childbearing potential.

All sexually active male subjects must agree to prevent potential transfer of and exposure to drug through semen to their partners by using a condom consistently and correctly, beginning with the first dose of study treatment and continuing for at least 6 months after the last dose of cisplatin and 30 days after the last dose of avelumab/placebo (whichever is later).

#### **4.4. Sponsor's Qualified Medical Personnel**

The contact information for the sponsor's appropriately qualified medical personnel for the study is documented in the study contact list located in the supporting study portal.

To facilitate access to appropriately qualified medical personnel on study-related medical questions or problems, patients are provided with a contact card. The contact card contains, at a minimum, protocol and investigational compound identifiers, patient study numbers, contact information for the investigational site, and contact details for a contact center in the event that the investigational site staff cannot be reached to provide advice on a medical question or problem originating from another healthcare professional not involved in the patient's participation in the study. The contact number can also be used by investigational staff if they are seeking advice on medical questions or problems; however, it should be used only in the event that the established communication pathways between the investigational site and the study team are not available. It is therefore intended to augment, but not replace, the established communication pathways between the investigational site and the study team for advice on medical questions or problems that may arise during the study. The contact number is not intended for use by the patient directly, and if a patient calls that number, he or she will be directed back to the investigational site.

